## IRB Minimal Risk Protocol Template

**Note: If this study establishes a human specimen repository (biobank) for research purposes, do not use this template. Use the Mayo Clinic Human Specimen Repository Protocol Template found on the IRB home page under Forms and Procedures at <http://intranet.mayo.edu/charlie/irb/>**

**First-time Use:** Use this template to describe your study for a new IRB submission.

1. Complete the questions that apply to your study.
2. Save an electronic copy of this protocol for future revisions.
3. When completing your IRBe application, you will be asked to upload this template to the protocol section.

**Modification:** To modify this template after your study has been approved:

1. Open your study in IRBe. Click on the study 'Documents' tab and select the most recent version of the protocol. Save it to your files.
2. Open the saved document and activate "Track Changes".
3. Revise the protocol template to reflect the modification points, save the template to your files
4. Create an IRBe Modification for the study and upload the revised protocol template.

## Purpose

**Hypothesis:** Early use of a vascular boot warming program plus standard anticoagulation can be a safe and effective method to resolve DVT±PE earlier and prevent development of post-thrombotic syndrome.

## **Aims, purpose, or objectives:**

### **Primary Objective**

1. The primary objective is to demonstrate whether a vascular boot warming program plus standard anticoagulation over standard anticoagulation can improve resolution of DVT±PE and functional performance in patients with deep vein thrombosis of the lower extremity ± pulmonary embolism.

### **Secondary Objectives**

1. Determine if early vascular boot warming plus standard anticoagulation (after 24 hours of anticoagulation therapy from time of diagnosis) is a safe intervention after diagnosis of acute DVT±PE.
2. Determine if vascular boot warming plus standard anticoagulation improves or accelerates the resolution of the clot among those with DVT±PE.
3. Determine if vascular boot warming plus standard anticoagulation improve the venous functional study measures of calf pump ejection fraction, VFR, PDR T90, and overall venous performance score.
4. Determine whether a vascular boot warming plus standard anticoagulation can improve the quality of life in patients with venous insufficiency or previous history of deep vein thrombosis of the lower extremity ± PE.
5. Identify difference in activity level between those who underwent a vascular boot warming program/activity plus standard anticoagulation versus standard anticoagulation only.
6. Analyze whether shear wave elastography will provide a more accurate and reliable method to assess the age of thrombosis and better quantification of thrombosis resolution.
7. Collect natural history data of post-thrombotic syndrome.

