#### Baseline studies will include:

- (1) Venous plethysmography: (ejection fraction, VFR, PDR T90, EDV T90, MV, F1.0).
- (2) Lower Extremity Ultrasound: DVT (thrombus) evaluation with 2-D ultrasonography (standard) and shear wave elastography (done within 1 day of baseline clinical ultrasonography).
- (3) Other relevant clinical information (such as height, weight, BMI, bilateral calf circumference, edema, leg pain, ulcerations, previous LE surgery, use of compression stockings, and any current set exercise program). Demographical data, common vascular risk factors (including tobacco use, coronary and peripheral arterial occlusive disease, diabetes, hypercholesterolemia, and hypertension) and the treatment information, will be obtained from chart review via ACE database and Synthesis. All data will be entered and stored in RedCap research tool.
- (4) Anatomic distribution of thrombi at initial examination will be documented as single segment and/or multi-segment(s) involved. The segments will be label as: external iliac vein (EIV), only if clot extends above the common femoral vein; common femoral vein (CFV); femoral vein (FV) (upper, middle, lower); deep femoral vein (DFV); popliteal vein (PV); posterior tibial vein (PTV); gastrocnemius (G-calf); peroneal vein-calf (PV-calf); soleal vein-calf (SV-calf) (see Table 1).

Table 1.0

Site	Anatomic Distribution of Thrombi			
	Initial	3 days	10 days	3 months
Single Segments				
External Iliac (EIV); if evaluated				
Common femoral (CFV)				
Femoral- Upper (FV)				
Femoral - Middle				

Femoral - Lower				
Deep Femoral (DFV)				
Popliteal (PV)				
Posterior Tibial (PT-calf)				
Gastrocnemius (G-calf)				
Peroneal (P-calf)				
Soleal (S-calf)				
Total				
Multisegment				
EIV- CFV				
EIV- CFV-FV				
EIV- CFV-FV-PV				
EIV- CFV-FV-PV-calf				
CFV-FV				
CFV-FV-PV				
CFV-FV-PV-calf				
FV-PV				
FV-PV-calf				
Total				

Patient will then be randomized to vascular boot plus standard anticoagulation program or standard anticoagulation using the randomizer built into RedCap.

**Standard of Care (SOC) Group (no vascular boot utilized)**: Patients will receive standard anticoagulation (determined at discretion of the treating provider), baseline studies, and follow up at the end of treatment (3months).

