**Vascular Boot (VB) Group (includes vascular boot in addition to SOC)**: Patients will receive standard anticoagulation (determined at discretion of the treating provider), baseline studies and standardized vascular boot warming (see below). All patients randomized to this group will wear the vascular boot for a minimum of 30 minutes per day for the first 10 days of participation. Patients in this group may initially be enrolled at either the thrombophilia clinic or the hospital.

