**Standardization of the vascular boot warming:**

The vascular boot is designed to completely surround the foot, heel and calf, insulating the limb. For each vascular boot session, the following data will be recorded:

- (1) Total duration of wearing vascular boot during first 10 days of study participation
- (2) Affected leg pain measured on a 0-10 scale at initial vascular boot warming (baseline) and every day during the calf warming while participating in the study.

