**Follow up data (SOC and VB Groups) include:**

- (1) Ultrasound of the leg with DVT and leg circumference measurement at 3 days, 10 days, and 3 months. Ultrasound data will include data on thrombus resolution, such as size and recanalization present.
- (2) Venous plethysmography at 3 months.
- (3) Study Questionnaires:
  - a. Godin questionnaire (validated questionnaires to measure physical activity)
  - b. VEINES-QOL (generic physical quality of life questionnaire)
  - c. Villalta Score (to assess Post-Thrombotic Syndrome)

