**Study Procedure**

All subjects included in this study will have a diagnosis of deep vein thrombosis that will undergo standard anticoagulation with or without wearing a vascular boot. Medical charts will be abstracted for clinical, laboratory, medications, imaging and pathologic findings. Subjects will undergo their initial (baseline) clinically indicated DVT ultrasound for diagnosis of lower extremity DVT. The second clinically indicated limited venous ultrasound will be completed on post-DVT day 90 (14±days) to evaluate resolution. Research ultrasound intervals will then occur on days 0 (+1 days), 3 (-2/+5 days), 10 (±5 days), and 90 (14±days). Shear wave elastography will be conducted at all post-treatment ultrasound intervals. We will compare the shear wave elastography to the opposite lower extremity veins on the same individual for a control if DVT is not present in that extremity at that time or previously.

Commercially available ultrasound systems (Logiq E9, GE Medical Systems, Milwaukee, WI, USA) equipped with phased-array and linear transducers will be utilized. Longitudinal and short axis images of each clot will be acquired and digitally stored for offline analysis. The short axis images will be acquired. 2-D images, 2D shear wave and elastography images will be acquired and digitally stored for off-line analysis. All measurements will be made in a blinded fashion by a single observer.

**Shear Wave Elastography:** The subject will be asked to lay on a hospital bed for ultrasound imaging. The veins of the lower extremity will be visualized using ultrasound imaging, and the depth of the venous wall will be noted. The focal depth on the device will be set to measure shear wave propagation in the walls of the vein and in the thrombus. Measurements will be made at multiple locations along the veins length.

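### Safety is a stated objective, but no outcome is designated as safety, and bleeding, new PE and skin injury are not prospectively collected in either arm

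*Combined protocol and SAP*

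**What the plan says.** All references are to the combined protocol and SAP.

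- **Objective.** The hypothesis under Purpose is that boot warming plus anticoagulation "can be a safe and effective method to resolve DVT±PE earlier". Secondary Objective 1 is to determine whether the early intervention "is a safe intervention after diagnosis of acute DVT±PE".
- **Endpoints.** The primary endpoint is resolution on ultrasound. The secondary endpoints are plethysmography, three questionnaires (Godin, VEINES-QOL, Villalta) and shear wave elastography. The Data Analysis Plan names no safety analysis.
- **Boot arm.** Patients "will wear the vascular boot for a minimum of 30 minutes per day for the first 10 days of participation" (Vascular Boot Group). Session data are wear time and leg pain on a 0-10 scale, taken at the first session and "every day during the calf warming while participating in the study" (Standardization of the vascular boot warming).
- **Both arms.** Follow up data lists "Ultrasound of the leg with DVT and leg circumference measurement at 3 days, 10 days, and 3 months", plethysmography at 3 months, and the three questionnaires with no visit given. Study Procedure adds: "Medical charts will be abstracted for clinical, laboratory, medications, imaging and pathologic findings".
- **Timing.** Study Procedure states: "Research ultrasound intervals will then occur on days 0 (+1 days), 3 (-2/+5 days), 10 (±5 days), and 90 (14±days". The Standard of Care Group paragraph mentions only "follow up at the end of treatment (3months" by way of follow-up timing.

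**The concern.** An objective that asks whether an intervention is safe needs at least one outcome that can answer it, gathered in the same way in both arms. Here none is designated. An analyst following the plan exactly would reach Secondary Objective 1 with ultrasound grades, leg circumference, a post-thrombotic score and whatever happened to be in the chart. The chart has no event definition or time window to work to.

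Pain is also recorded unequally: boot patients have a score for each day of warming, while standard-care patients have no planned follow-up score. None of this can be repaired reliably after follow-up ends. With so few patients, a single missed event changes the result.

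**Working it through.** **1. Match the objective to what is collected.**

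| Item | Where it appears | Arms in follow-up | Designated as safety? |
|---|---|---|---|
| Thrombus worsening or extension | Table 2; scans under Follow up data | Both | No |
| Leg circumference | Follow up data, item 1 | Both | No |
| Villalta score | Follow up data, item 3; secondary endpoint ii | Both, no visit stated | No, listed under quality of function |
| Charted findings | Study Procedure | Both, no event or window defined | No |
| Daily leg pain, 0-10 | Standardization of the vascular boot warming | Boot only | No |
| New PE | CT mentioned only for diagnosis at entry (Subject population) | Not planned | n/a |
| Bleeding | Nowhere | Not planned | n/a |
| Skin injury | Ulcerations in the baseline list only | Not planned | n/a |

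The last three rows are examples of events that a safety question would ordinarily cover. The documents do not name them as expected harms of the boot.

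**2. Visit windows, which matter for the repair.** From Study Procedure, reading the last window as plus or minus 14 days:

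- Day 3: 3 - 2 = 1 to 3 + 5 = 8.
- Day 10: 10 - 5 = 5 to 10 + 5 = 15.
- Day 90: 90 - 14 = 76 to 90 + 14 = 104.

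If study days and boot days start together, a day-10 visit held on day 5 leaves 10 - 5 = 5 of the 10 boot days still ahead. A last visit on day 76 leaves 90 - 76 = 14 days unobserved before day 90, with no later contact planned.

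**3. What 15 per arm can show.** The plan has no safety figure to reproduce. Its target of 30 is 15 + 15, and the Data Analysis Plan says it was not calculated.

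- 0 of 15, exact two-sided 95% upper limit: 1 - 0.025^(1/15) = 0.218.
- 1 of 15, exact 95% interval: 0.2% to 31.9%.
- 0 of 15 in both arms, Newcombe 95% interval for the difference: -20.4 to +20.4 percentage points.
- Chance of at least one event among 15 boot patients: 1 - 0.95^15 = 0.537 at a true rate of 5%, and 1 - 0.90^15 = 0.794 at 10%. Both rates are assumptions.
- Fisher's exact test: 4 v 0 events gives p = 0.100 and 5 v 0 gives p = 0.042, so five events against none is the smallest such split below 0.05.

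**4. Questionnaires (the separate, minor point).** No questionnaire is in the baseline list and none has a stated visit. The correlation r between baseline and follow-up is not in the documents, so a range is assumed. Mean 95% half-widths for the arm difference, in SD units, come from 40,000 simulated trials per r with 15 per arm:

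- Follow-up scores only: 0.741 (check with SD fixed at 1: t with 28 df x sqrt(2/15) = 0.748).
- Adjusted for baseline by ANCOVA: 0.753, 0.721, 0.655 and 0.540 at r = 0.1, 0.3, 0.5 and 0.7.

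**The case against.** The strongest reply is that this is a 30-patient pilot on a minimal-risk template whose Statistical Information note says that pilots need no endpoints, and that no addition to the data could establish safety at this size. The second half stands: even a perfect form leaves 0 of 15 compatible with a true rate near 22%. The first half does not remove the gap, because this protocol chose to state a safety objective and wrote its own Endpoints section.

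A second reply is that relevant data are already collected in both arms. That is partly right. A reader might infer that the trial gathers nothing on safety, or nothing but thrombus extension. The documents do not support that: leg circumference and Villalta are follow-up items for both groups, and charts are abstracted for all. They are undesignated and incomplete, but they exist.

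Three other tempting readings also go too far:

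- *Standard-care patients are not seen until 3 months.* The Standard of Care Group paragraph mentions 3 months but does not exclude earlier visits. Follow up data covers both groups at 3 days, 10 days and 3 months, and Study Procedure does not separate the arms. The wording needs clarifying; it does not show that visits are missing.
- *Bleeding, PE or skin events will be over-reported in the boot arm.* Only pain is demonstrably recorded unequally. The session record has no field for the other events, so the rest is conjecture.
- *The extension grade is protected by blinding.* Study Procedure says that measurements are blinded, directly after describing images stored for off-line analysis. It does not say whether this covers the Table 2 grading, which relies on compressibility and flow.

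**Conclusion.** The gap is real and worth correcting. Safety is in the hypothesis and is Secondary Objective 1, but no endpoint or analysis is designated as safety. Prospective follow-up collection of bleeding, new PE and skin injury is not planned in either arm, and daily leg pain is recorded in the boot arm only. As written, the objective would be answered from incidental two-arm data.

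The size of the problem is one objective without a proper outcome; it does not invalidate the efficacy comparison. Better collection would permit a fair description and no more (0 of 15: upper limit 21.8%). The exact limits need only the planned 15 per arm; the 54% and 79% chances of seeing an event rest on assumed rates.

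The questionnaire point is separate and minor. A reader might infer that a missing baseline biases the result. It does not: comparing follow-up scores between randomised arms remains valid. The possible loss is precision, and at an assumed correlation of about 0.3 or lower there is little or nothing to gain.

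**What to change.** **Main change.**

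- Use one short, dated event checklist in both arms at the existing 3-day, 10-day and 3-month contacts. It might cover thrombus extension, new confirmed PE, bleeding and skin injury. Record the same 0-10 leg pain score in both arms at those contacts.
- Count events through day 10, completing the count at the next contact when the visit falls before day 10. Also count through the 3-month visit and report each patient's follow-up time. A fixed day-90 count would be incomplete for anyone last seen on days 76 to 89.
- State whether the blinding covers the Table 2 grading.
- Reconcile the Standard of Care Group wording with Follow up data and Study Procedure, so that attendance at days 3 and 10 is explicit.
- Report counts by arm with exact 95% intervals, and reword Secondary Objective 1 as describing safety.

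**Minor change.** State the visit for each questionnaire. Give Godin and VEINES-QOL before randomisation and at 3 months, and compare the arms with baseline adjustment; the Data Analysis Plan already allows covariance regression modelling.

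**Cost.** A one-page form, a pain score, two questionnaires at baseline and some rewording. Patient burden rises slightly, and events between contacts depend partly on recall. The sample size and the treatment in either arm do not change.

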**Statistical Considerations**

**Data Analysis Plan:**

This is a pilot study including 30 volunteers. Sample size cannot be calculated statistically due to lack of prior studies in the literature for those with DVT and use of warming boot. We will recruit up to 30 subjects who have valid measurements as described in the Data Analysis plan.

The ultrasound measurements (elastography) will be assessed for validity using data analysis techniques and to examine the visualization of the venous wall to see if we can quantify the thrombosis.

All statistical tests will be 2-tailed at a significance level of  $P < 0.05$ . Demographic and physical characteristics laboratory values and comorbid conditions will be presented as mean  $\pm$  standard deviation for continuous variables and as frequencies and percentages for categorical variables. Counts and percentages will be presented for categorical variables, while means  $\pm$  standard deviations and 95% confidence intervals will describe continuous variables for which normality assumptions are met. If the distribution of a continuous parameter is skewed, transformations will be considered, or medians and interquartile ranges (IQR) will be presented. Continuous variables will be compared between 2 groups using unpaired t-tests. For comparison of continuous variables in  $\geq 3$  groups, one-way analysis of variance (ANOVA) followed by a Scheffé test may be performed. Frequencies will be compared using Chi square analysis. The correlation between 2 continuous variables will be determined using a linear regression analysis. Cox proportional hazards regression will be used to estimate the

association between thrombosis and short-term and long-term outcomes. Logistic regression will be used to estimate the association between thrombosis and binary outcomes. Adjustment for potential confounders will be accomplished through, either, covariance regression modeling, propensity score stratification, or propensity matching, according to the discretion of the statistical analyst. Statistical analyses will be performed using SAS and/or R software.

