### **Secondary:**

- i. Improvements in calf muscle function as measured by venous plethysmography (ejection fraction, VFR, PDR T90, EDV T90).
- ii. Improved quality of function : Godin questionnaire (validated questionnaires to measure physical activity), VEINES-QOL (generic physical quality of life questionnaire) and Villalta Score (to assess Post-Thrombotic Syndrome)
- iii. Analyze whether shear wave elastography will provide a more accurate and reliable method to assess the age of thrombosis and better quantification of thrombosis resolution.

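### Taking the Godin score before randomisation and adjusting for it could sharpen the activity comparison, if baseline and follow-up scores correlate above about 0.2

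*Combined protocol and SAP*

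**What the plan says.** Secondary Objectives, item 5, asks for a between-arm comparison of activity level: "Identify difference in activity level between those who underwent a vascular boot warming program/activity plus standard anticoagulation versus standard anticoagulation only". It names no instrument. The instrument comes from secondary endpoint ii, "Improved quality of function : Godin questionnaire (validated questionnaires to measure physical activity", and from item 3 of the follow-up data, "Godin questionnaire (validated questionnaires to measure physical activity".

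In that follow-up list, ultrasound has three visits (3 days, 10 days, 3 months) and plethysmography has one: "Venous plethysmography at 3 months". The questionnaires have none. The closest statement is in the description of the standard-of-care group, which has "follow up at the end of treatment (3months".

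The baseline list has four items: plethysmography, leg ultrasound with elastography, clinical and demographic information, and the anatomic distribution of thrombus. Godin is in none of them. The only entry touching on activity is in the third item: "use of compression stockings, and any current set exercise program". Allocation comes after these studies: "Patient will then be randomized to vascular boot plus standard anticoagulation program or standard anticoagulation".

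The Data Analysis Plan states: "Continuous variables will be compared between 2 groups using unpaired t-tests". Tests are two-sided at 0.05. For confounders that it does not name, the plan also offers covariance regression or one of two propensity-score methods, at the analyst's choice. Target accrual is 30, with 15 per arm.

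**The concern.** Followed as written, the plan yields one Godin score per patient, at an unstated time after randomisation, compared between two groups of 15. Randomisation makes that comparison fair, but at this size it is imprecise. The usual remedy is to adjust for the same measure taken before allocation. That is closed off here, because no later choice of model can recover a score that was not collected. The exercise-program entry is coarser and is not on the Godin scale.

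Two things are at stake. One is the precision of objective 5. The other is information for a later trial: without a baseline score the pilot cannot estimate the correlation between baseline and follow-up Godin, even roughly, and a larger trial would want that figure for planning.

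**Working it through.** **Inputs.** 15 per arm (Target accrual); two-sided alpha 0.05 and an unpaired t-test (Data Analysis Plan). The documents state no power, effect size, SD or correlation for Godin, so there is no planned figure to reproduce. Results are in SD units, with r, the baseline-to-follow-up correlation, as an assumption shown over a range. Normal scores and a linear relation to baseline are also assumed.

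**Planned test (28 df).**
- Standard error = √(2/15) = 0.365 SD.
- 95% CI half-width = t(0.975, 28) × 0.365 = 2.048 × 0.365 = 0.748 SD.
- Difference detectable with 80% power (noncentral t, noncentrality = difference / standard error): 1.06 SD. Power is 26% for a true difference of 0.5 SD and 56% for 0.8 SD.

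**ANCOVA on baseline Godin (27 df).** The variance is multiplied by (1 − r²) × (1 + 1/(N − 4)). With N = 30 the second factor is 1 + 1/26 = 1.038, the price of estimating the slope in a small sample. The half-width is 2.052 × √[(2/15)(1 − r²)(1.038)]. At r = 0.5 this is 2.052 × √(0.1333 × 0.75 × 1.038) = 2.052 × 0.322 = 0.661 SD.

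**Change-score t-test (28 df).** The variance is multiplied by 2(1 − r).

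| Analysis | Half-width (SD) | Relative to planned | Detectable difference (SD) | Power at 0.8 SD |
|---|---|---|---|---|
| Planned t-test | 0.748 | 1.00 | 1.06 | 56% |
| ANCOVA, r = 0 | 0.763 | 1.02 | 1.08 | 55% |
| ANCOVA, r = 0.3 | 0.728 | 0.97 | 1.03 | 58% |
| ANCOVA, r = 0.5 | 0.661 | 0.88 | 0.94 | 67% |
| ANCOVA, r = 0.7 | 0.545 | 0.73 | 0.77 | 83% |
| Change score, r = 0.3 | 0.885 | 1.18 | 1.25 | – |
| Change score, r = 0.5 | 0.748 | 1.00 | 1.06 | – |
| Change score, r = 0.7 | 0.579 | 0.77 | 0.82 | – |

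**Break-even.** ANCOVA and the t-test give equal half-widths when 2.052² × (1 − r²) × 1.038 = 2.048², that is, at r ≈ 0.20.

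**In patients.** At r = 0.5 the ANCOVA is worth 15 / (0.75 × 1.038) ≈ 19 per arm.

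**Simulation check** (10,000 trials at each r). The ratio of ANCOVA to t-test half-width was 1.02, 0.97, 0.88 and 0.73 at r = 0, 0.3, 0.5 and 0.7. Type I error was 4.8% to 5.4% for the t-test and 4.6% to 5.2% for ANCOVA, so both are valid.

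**Sensitivity.** If only 12 per arm gave a Godin score (an assumption; no dropout rate is stated), the t-test half-width would be 0.85 SD, ANCOVA at r = 0.5 would give 0.75 SD, and break-even would be at r ≈ 0.23.

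**The case against.** The strongest reply is that nothing is broken. Objective 5 asks for a difference between arms, and a randomised follow-up comparison answers that without a baseline. The study is a 30-patient pilot, and the Statistical Information section says that pilots need no power analysis. All of this stands, and it limits the point to an optional gain.

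- **The plan already allows covariance regression.** True, so the t-test is not the only analysis open. Skewed data may also be transformed or summarised by medians. But the adjustment is for unnamed confounders, and there would be no baseline Godin to put in the model.
- **The 3-month visit is the natural reading.** Probably so, given the standard-of-care follow-up and the plethysmography visit, but no text ties Godin to it. A score at 3 or 10 days would fall around the 10 days of boot wear and measure something different.
- **There may be another source of activity data.** An exclusion criterion mentions a log covering activity or boot wear. The wording is ambiguous. A log kept during the study could not in any case serve as a pre-randomisation covariate.
- **Objective 5 is not the worst affected.** VEINES-QOL and Villalta are also missing from the baseline list, and objective 4 is worded as improvement. That is fair, but it does not remove the gap for Godin.
- **Recall may be poor.** Baseline falls within days of an acute DVT, so patients would be reporting earlier activity from memory. This could hold r down. At r = 0.3 the interval narrows by only about 3%, and below about 0.2 it does not narrow at all.

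**Conclusion.** The point holds as a low-cost improvement. The Godin score is not collected before randomisation and has no stated visit, so objective 5 rests on a valid but imprecise comparison of 15 with 15 (half-width about 0.75 SD). Baseline Godin with ANCOVA could reduce the half-width by about 3%, 12% or 27% at r = 0.3, 0.5 or 0.7. The worst case is about 2% wider at r = 0. These figures rest on assumed correlations, normal scores and complete data. Even at r = 0.7 only differences of about 0.8 SD are detectable with 80% power.

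A reader might infer three stronger things that the documents do not support:
- That the planned test is biased or invalid. Allocation is randomised, and the simulated type I error is nominal.
- That objective 5 cannot be answered without a baseline. It asks for a between-arm difference, not for change. Endpoint ii speaks of improvement, and change from baseline on Godin indeed could not be reported, but that wording can also mean a better result in the boot arm.
- That adjustment is certain to help. The documents give no correlation, and the gain needs r above about 0.2.

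**What to change.** 1. Add Godin to the baseline studies, completed before randomisation, with patients asked about their usual activity before the DVT.
2. In the follow-up data, state that Godin is repeated at the existing 3-month visit.
3. In the Data Analysis Plan, name 3-month Godin as the measure for objective 5. Compare it between arms by ANCOVA with baseline Godin as covariate, and report the difference with a 95% CI.
4. Do not use a change-score test. It has a wider interval than ANCOVA at every r in the table. Change from recalled pre-DVT activity would also describe return to usual activity, not recovery from the acute state.

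The cost is one short questionnaire at a baseline visit that already takes place, a few lines of text, one degree of freedom and some recall noise. No patients or visits are added. The pilot would also gain an estimate of r for planning, though a rough one from 30 patients. The change has to be made before enrolment, since the baseline score cannot be obtained before allocation once a patient has been randomised.
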